9.2.5 Cardiovascular and death events

Not Applicable for this trial.

9.2.6 Pregnancies and associated adverse events

Details of pregnancies in female subjects and, female partners of male subjects (paternal) will be collected after the first-trial-related activity after obtaining informed consent and until end of trial visit.

If a pregnancy is reported in female subjects, the investigator should inform Novo Nordisk within 14 calendar days of learning of the pregnancy and should follow the procedures outlined in [Appendix 5](#).

Pregnancy outcome should be documented in the subject's medical record. Abnormal pregnancy outcome (e.g. spontaneous abortion, foetal death, stillbirth, congenital anomalies and ectopic pregnancy) is considered an SAE.

9.2.7 Medical device incidents (including malfunctions)

[figure not shown]
Not applicable for this trial. Refer to technical complaints in section [9.2.8](#).

9.2.8 Technical complaints

The investigator must assess whether a technical complaint is related to an AE.

The definitions and reporting process for technical complaints can be found in [Appendix 6](#).

Timelines for reporting technical complaints are listed in [Figure 3](#).

AE: Adverse Event, SAE: Serious Adverse Event, SIF: Safety Information Form

Figure 3 Decision tree for determining the forms to complete with associated timelines for technical complaints.

9.3 Treatment of overdose

There is no antidote for overdose of somapacitan or Norditropin®. In the event of an overdose, appropriate supportive treatment should be initiated according to local practice.

Accidental overdose must be reported as a medication error. Refer to Section 9.2.1 for further details.

In the event of an overdose, the investigator should closely monitor the subject for overdose-related AE/SAE and laboratory abnormalities until resolved.

For more information on overdose, also consult the current version of the somapacitan and Norditropin® investigator's brochures¹³.

9.4 Safety assessments

Planned time points for all safety assessments are provided in the flowchart Section 2.

A **concomitant illness** is any illness that is present at the start of the trial (i.e. at the first visit) or found as a result of a screening procedure or other trial procedures performed before exposure to trial product.

Medical history is a medical event that the subject has experienced in the past.

In case of an abnormal and clinically significant finding, the investigator must record the finding on the Medical History/Concomitant Illness form if it is present at screening. Any new finding fulfilling the AE definition (see Appendix 4) during the trial and any clinically significant worsening from baseline (Visit 2) must be reported as an AE (see Section 9.2).

GHD history

- Type of GH stimulation tests and result of peak GH values

- Standing height measured minimum 6 and maximum 18 months prior to screening. Standing height should be reported in centimetres with one decimal to the nearest 1 mm or in inches with one decimal. The pre-trial height assessment is collected to be used when evaluating inclusion criterion 5 and for baseline HV derivation.
- Parental height: Standing height for both biological parents in centimetres with one decimal to the nearest 1 mm or in inches with one decimal.

9.4.1 Physical examinations

A physical examination will include assessments of the Cardiovascular, Respiratory, Gastrointestinal, Musculoskeletal, Central and Peripheral Nervous system and Skin systems, head, ears, eyes, nose, throat, neck and lymphnode palpation. Investigators should pay special attention to clinical signs related to previous serious illnesses.

9.4.2 Vital signs

Blood pressure and pulse measurements will be assessed in sitting position with a completely automated device. Manual techniques will be used only if an automated device is not available.

9.4.3 Electrocardiograms

12-lead ECG will be obtained as outlined in the flowchart [2](#).

The investigator will evaluate the ECG recordings and classify them as either: “normal”, “abnormal, not clinically significant” or “abnormal, clinically significant”.

If the ECG is evaluated as “abnormal, clinically significant” at screening, and judged by the investigator not to be relevant for exclusion of the trial, the finding will be recorded as a concomitant illness.

The ECG results must be dated and signed by the investigator to verify that the data have been reviewed.

9.4.4 MRI and CT scans

An MRI or CT scan of the brain performed according to standard practice at site must be available before randomisation, to confirm eligibility in relation to inclusion criterion 11. A scan or imaging performed within 9 months prior to screening can be used as screening data if medical evaluation and conclusion is available.

The only information collected in the eCRF is subject eligibility for trial participation.

For France: See [Appendix 9](#).

9.4.5 Clinical safety laboratory assessments

All protocol-required laboratory assessments, as defined in [Appendix 2](#), must be conducted in accordance with the laboratory manual and the flowchart in Section [2](#).

9.4.6 Immunogenicity assessments

All anti-drug antibody (ADA) samples must be drawn prior to trial product administration if trial product administration is planned on the sampling day.

A tiered approach including screening of samples, confirmation of anti-drug antibodies as well as characterisation of cross-reactivity towards endogenous hGH and in vitro neutralising activity against the trial product will be used. To evaluate the impact of antibody formation, results of antibody analyses will be compared to PK and pharmacodynamics (PD) markers.

The investigator will not be able to review the results of the antibody measurements in relations to AEs as the results will not be available to the investigator.

In a case of two consecutive positive antibody tests the Novo Nordisk safety committee see [Appendix 3](#) will assess if the antibodies have an impact on the efficacy and/or safety. The investigator will be informed, after a Novo Nordisk safety committee assessment if any clinically relevant impact on efficacy and/or safety.

All subjects who have had two consecutive positive antibody test results (high titer and/or persistent in vitro neutralising antibody response) will be offered an appropriate follow-up period until the antibody response remains unchanged, is decreasing or until the investigator or the sponsor decides that no further follow-up is warranted. During the trial this will be covered by regular anti-drug antibody sampling, and after last patient last visit, the subjects may be requested to have additional blood samples collected for follow-up analyses.

The results may be reported as an amendment to the clinical trial report (CTR).

9.4.6.1 Anti somapacitan antibodies

Determination of antibodies against somapacitan in subjects randomised to somapacitan will be performed by a special laboratory using a validated binding antibody assay. Confirmed anti-somapacitan antibody positive samples will be further tested for cross-reactivity to hGH and for in vitro neutralising effect in a validated neutralising antibody assay and by correlation to PK/PD.

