^bThe follow-up visit should also be performed after Visit 19A for subjects who discontinue treatment. The Follow-up visit can be performed as a phone visit.

^c Demography consists of date of birth, sex, ethnicity and race (according to local regulation, for Spain, please refer to [Appendix 9](#))

^dNot to be done if performed within the last 6 months

^eSubjects on Norditropin® will be switched to somapacitan

^fOnly applicable for subjects in France. Not to be done if performed within the last 6 months

3 Introduction

Throughout the protocol, the term subject refers to the subject and the parent or legally acceptable representative (LAR) as a whole if applicable, depending on the age and the capability of the subject to perform the required trial procedures.

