5.1 Overall design

A randomised open-labelled two arm (somapacitan and Norditropin[®]) trial designed to compare the effect and safety of once weekly dosing of somapacitan with daily dosing of Norditropin[®] after 52 weeks in children with growth hormone deficiency followed by a 3 year single-arm extension period with once weekly dosing of somapacitan to evaluate safety. The randomisation will be stratified by region (Japan versus rest-of-the-world) as well as age group (< 6 versus ≥ 6 years at randomisation), gender (boys versus girls) and growth hormone peak level (< 7.0 versus ≥ 7.0 ng/ml) to ensure equal distribution of these factor levels across treatments.

The total trial duration for a subject will be 4 years.

Eligible subjects will be randomised in a 2:1 manner to receive either somapacitan (2 out of 3 subjects) or Norditropin[®] (1 out of 3 subjects).

The follow-up period is a minimum of 30 days.

[figure not shown]

Figure 1 Trial design

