9.4.6.2 Anti hGH antibodies

Anti-hGH antibodies in subjects randomised to Norditropin[®] will be analysed by a special laboratory using a validated binding antibody assay. Confirmed anti-hGH antibodies will be further assessed for in vitro neutralising effect of anti-hGH antibodies in a validated neutralising antibody assay and by correlating to PK/PD.

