9.4.6.3 Assessment in case of suspicion of severe systemic hypersensitivity

In the event of a severe local and/or systemic hypersensitivity reaction possible or probably related to trial product, blood sampling for assessment of anti-somapacitan or anti-Norditropin[®] IgE antibodies as well as binding antibodies should be performed in relation to the reaction and no later than 1-2 weeks after the event.

In the event of a severe systemic hypersensitivity reaction to trial product it is recommended also to analyse a sample collected within 3 hours of the reaction for tryptase (total and/or mature tryptase) at the local laboratory. Moreover, a baseline tryptase measurement is necessary 1-2 weeks after the immediate severe hypersensitivity reaction due to individual variation in tryptase baseline concentration.

A follow up visit should be conducted 3-4 weeks after the allergic reaction with repeated blood sampling for assessment of anti-somapacitan or anti-Norditropin[®] IgE antibodies as well as binding antibodies and, if possible, also at a visit 3 months post the hypersensitivity reaction for assessing the persistence of the IgE response. Tryptase measurements are not required at the follow up visits.

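### Sections 9.4.6.1 and 9.4.6.2 assign the routine antibody assays by randomised arm and ignore the visit 7 switch, so as written about 58 switched children stay on the anti-hGH assay and get no routine anti-somapacitan assay in the extension

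*Combined protocol and SAP*

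**What the plan says.** Section 5.1 describes 52 randomised weeks followed by a "3 year single-arm extension period with once weekly dosing of somapacitan to evaluate safety". Footnote e to the flowchart (section 2) says that children on Norditropin "will be switched to somapacitan" at visit 7.

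Two sections assign the routine assays:
- 9.4.6.1: "Determination of antibodies against somapacitan in subjects randomised to somapacitan will be performed by a special laboratory".
- 9.4.6.2 opens with "Anti-hGH antibodies in subjects randomised to Norditropin" and sends those samples to a binding assay, then to a neutralising assay if confirmed positive.

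The further work in 9.4.6.1 starts from a confirmed positive in its own assay: "Confirmed anti-somapacitan antibody positive samples will be further tested for cross-reactivity to hGH", and for neutralising effect.

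Section 9.4.6.3 is not limited by arm but is driven by events. It applies "In the event of a severe local and/or systemic hypersensitivity reaction possible or probably related to trial product" and then asks for IgE and binding antibodies against the product concerned.

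Section 9.4.6 sets out what follows a positive result. It begins "In a case of two consecutive positive antibody tests the Novo Nordisk safety committee" and has the committee judge the effect on efficacy and safety. On follow-up of positive children it says: "During the trial this will be covered by regular anti-drug antibody sampling".

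The flowchart has one antibody row for all subjects, running into the extension. Table 6 (Appendix 2) lists both assays without naming an arm. Table 7, the sampling-time table through visit 19A, is headed for the arm randomised to somapacitan.

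**The concern.** After visit 7 every child who stays in the trial takes somapacitan, and the extension exists to evaluate its safety. The assay rule still looks back to randomisation. A switched child is therefore assigned the assay for the product just stopped and not the assay for the product being taken.

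Three steps depend on the missing assay. Cross-reactivity and neutralisation testing under 9.4.6.1 need a confirmed anti-somapacitan positive. The safety committee's review needs two consecutive positives. Follow-up of a positive child during the trial relies on routine sampling. From a switched child's routine samples, none of these could start for antibodies specific to somapacitan. Section 9.4.6 also withholds antibody results from investigators, so a site would be poorly placed to notice the gap.

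Switched children meet somapacitan after a year of daily hGH, a history that the continuing arm does not share. The documents give no data on whether that changes the antibody response, which is a reason to measure it rather than to infer it from the continuing arm.

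**Working it through.** **1. Inputs.** About 192 randomised (5.2); 2:1 allocation (5.1); 10% per arm off randomised treatment or without visit 7 data (10.1), made up of 5% who stop treatment but have visit 7 data and 5% with no visit 7 data. Under 8.1, children who stop treatment before visit 7 are followed to that visit and then withdrawn, so neither group enters the extension.

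**2. The plan's own figure.** With margin 1.8, SD 3.5, one-sided 2.5%, 90% power and 2:1 allocation, controls = (1.960 + 1.282)² x 3.5² x 1.5 / 1.8² = 59.6, rounded up to 60. Allowing for 5% without visit 7 data, 60/0.95 = 63.2, rounded up to 64, so the total is 3 x 64 = 192, as stated. The per-protocol size of 54 in 10.1 agrees: 64 x 0.85 = 54.4.

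**3. Children switched.** The plan does not state this number.
- Norditropin arm: 192/3 = 64.
- Switched at visit 7: 64 x 0.90 = 57.6, about 58.
- Extension total: 192 x 0.90 = 172.8, about 173.
- Share: 57.6/172.8 = one third.
- Assumed range for loss before visit 7: at 15%, 64 x 0.85 = 54; at 5%, 64 x 0.95 = 61.

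**4. Routine antibody visits in the extension.** The flowchart columns are damaged in the available text. Aligning the antibody row with the yearly ECG row (visits 7, 11, 15, 19) places extension antibody samples at visits 9, 11, 15 and 19. The blood volumes in Table 4 agree: visit 9 draws 11 mL, as visit 5 does, while visits 13 and 17 draw 9 mL.

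**5. Samples affected.** 58 x 4 = 232 of 173 x 4 = 692, about one third. These counts assume that nobody leaves during the extension, so they are ceilings. The one-third share holds if dropout is similar in the two groups.

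**6. What each rule gives a switched child, read as written.**

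| Rule | Result |
|---|---|
| 9.4.6.1 | Not assigned; no follow-on testing from it |
| 9.4.6.2 | Anti-hGH binding assay continues, then neutralising assay if confirmed |
| 9.4.6.3 | Anti-somapacitan testing, but only after a severe hypersensitivity reaction |
| Flowchart, Table 6 | Sample drawn; assay not allocated to any group |
| Table 7 | Timing only; heading omits switched children |

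**The case against.** The best case on the other side is that the protocol means to test by current drug and is loosely worded. Section 7.1 pairs sampling for anti-somapacitan antibodies with somapacitan injection, with no limit by arm. Section 9.4.6 speaks of neutralising activity against the trial product, and in the extension the only trial product is somapacitan. Table 6 and the single antibody row carry no arm limit. Section 7.1 also has the Norditropin arm injecting daily for the whole trial, which cannot be literally true after visit 7. Section 9.4.5 defers to a laboratory manual as well as to the flowchart.

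This stands as evidence of intent, and a drafting slip is the likely explanation. It does not repair the rule. None of these texts allocates an assay to switched children, and the two sentences that do allocate assays use the randomised arm.

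The objection also bounds the harm. A reader might infer that switched children go without routine antibody testing, or that a response without a severe reaction would never be looked for. The documents do not support that. Under 9.4.6.2 their samples still go to the anti-hGH assays. Section 3.2.2 describes somapacitan as an hGH derivative with one point mutation, so antibodies that bind hGH would be sought and could reach the safety committee. What is left out is antibodies specific to somapacitan.

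The consequence is limited in other ways. Antibodies are not a listed endpoint, and the main-phase results planned for filing are unaffected because the switch comes at visit 7. Appendix 7 allows retained samples to be analysed later, but that is optional and too late for review during the trial.

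**Conclusion.** The concern holds as a defect in the stated rule. As written, about 58 children (54 to 61 over the assumed loss range), one third of those in the extension, have no routine anti-somapacitan assay while taking somapacitan. Their routine samples cannot start the follow-on tests in 9.4.6.1. Only the event-driven rule in 9.4.6.3 gives them an anti-somapacitan test.

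The count rests on 192 randomised, 2:1 allocation and the plan's own 10% loss. A reader might conclude that these children will in fact go untested for somapacitan-specific antibodies. The documents cannot show that, because the laboratory manual is not among them and may route the samples correctly. Nor do they support any number of missed cases. The point is worth correcting because the rule gives the wrong result in an extension run for safety, and the correction is small.

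**What to change.** - In 9.4.6.1, assign the anti-somapacitan assay to all subjects exposed to somapacitan, including those switched at visit 7.
- For switched children, use the visit 7 sample, drawn before the first somapacitan dose, as baseline, and run the assay on the antibody samples already scheduled later.
- Head Table 7 for subjects treated with somapacitan.
- Report extension antibody results separately for switched and continuing children.
- Check the laboratory manual against the revised text.

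The cost is up to 58 x 4 = 232 extra assays, or 58 x 5 = 290 with the baseline. Over the assumed loss range this runs from 54 x 4 = 216 without the baseline to 61 x 5 = 305 with it. All of these are ceilings that assume no dropout in the extension. No extra visit or blood draw is needed. The wording changes are short but need a protocol amendment with ethics committee approval (Appendix 3). If the manual already tests by current drug, only the wording and reporting change.

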9.4.6.2 Anti hGH antibodies

Anti-hGH antibodies in subjects randomised to Norditropin[®] will be analysed by a special laboratory using a validated binding antibody assay. Confirmed anti-hGH antibodies will be further assessed for in vitro neutralising effect of anti-hGH antibodies in a validated neutralising antibody assay and by correlating to PK/PD.

9.4.6.3 Assessment in case of suspicion of severe systemic hypersensitivity

In the event of a severe local and/or systemic hypersensitivity reaction possible or probably related to trial product, blood sampling for assessment of anti-somapacitan or anti-Norditropin[®] IgE antibodies as well as binding antibodies should be performed in relation to the reaction and no later than 1-2 weeks after the event.

In the event of a severe systemic hypersensitivity reaction to trial product it is recommended also to analyse a sample collected within 3 hours of the reaction for tryptase (total and/or mature tryptase) at the local laboratory. Moreover, a baseline tryptase measurement is necessary 1-2 weeks after the immediate severe hypersensitivity reaction due to individual variation in tryptase baseline concentration.

A follow up visit should be conducted 3-4 weeks after the allergic reaction with repeated blood sampling for assessment of anti-somapacitan or anti-Norditropin[®] IgE antibodies as well as binding antibodies and, if possible, also at a visit 3 months post the hypersensitivity reaction for assessing the persistence of the IgE response. Tryptase measurements are not required at the follow up visits.

9.5 Pharmacokinetics

Samples will be used to evaluate the pharmacokinetics of somapacitan and Norditropin[®].

All samples must be drawn prior to trial product administration if this is planned on a sampling day. The bioanalysis of somapacitan and Norditropin[®] PK samples will be performed by a special laboratory.

9.6 Pharmacodynamics

IGF-I and IGFBP-3 will be used to evaluate the PD of somapacitan and Norditropin[®]. Bioactive IGF-I is an exploratory analysis and will be measured at selected visits.

All samples must be drawn prior to trial product administration if this is planned on a sampling day.

9.7 Genetics

A blood sample for RNA (ribonucleic acid) analysis will be collected from subjects who have consented to participate in the genetic analysis component of the trial. Participation in the genetic research is optional. Subjects who do not wish to participate in the genetic research may still participate in the trial.

Genetic analyses will be used for exploratory purpose. The genetic data will be used, to evaluate a prediction model for growth response, for future purpose.

Results from genetic testing will not be reported to the sites since it will not be of clinical relevance. Only in the event that the findings show any results that may seriously affect the subject the site will be informed.

In the event of sample handling failure, a replacement genetic blood sample may be requested from the subject.

See [Appendix 8](#) for further information regarding the genetic research. Details on processes for collection, shipment and destruction of these samples can be found in the laboratory manual.

For country specific requirements see [Appendix 9](#).

9.8 Biomarkers

Not applicable for this trial.

10 Statistical considerations

10.1 Sample size determination

The sample size calculation is based on the primary estimand described in Section [4.2](#).

It is expected based on phase 2 trial data (NN8640-4172) that the proportion of subjects with no landmark visit data or who discontinued randomised treatment before landmark visit is 10% with similar withdrawal reasons in the two treatment arms (5% discontinuing randomised treatment but have landmark visit data and 5% withdrawn /lost to follow up with no landmark visit data). It is expected that subjects discontinuing their randomised treatment will start on ancillary treatment, if no medical reasons prohibits this. The term “retrieved subjects” will be used in this section as a short form for “subjects discontinuing randomised treatment but have landmark visit data”.

Assuming the same proportions of subjects with no landmark visit and retrieved subjects in the two arms leads to the following sample size calculation.

Primary estimand (FDA and PMDA)

The sample size is determined using a non-inferiority margin of 1.8 cm/year and a one sided two-group t-test with a significance level of 2.5% for a 2:1 randomisation ratio between somapacitan and Norditropin®.

As trial results from trials allowing ancillary therapy or having retrieved landmark data included in the analysis are limited, a conservative standard deviation for HV at week 52 was chosen (SD=3.5cm/year) and the different scenarios giving 90% power for the primary analysis are presented in the table below under the assumption of a true difference in annualized HV of 0 cm/year between the two treatment arms and no true difference in annualized HV between retrieved subjects and subjects staying on randomised treatment at landmark visit.

Table 3 Sample size for various standard deviations

SD	3.0 cm/year	3.25 cm/year	3.5 cm/year	3.75 cm/year
Primary estimand	144	171	192	219
(Treatment policy strategy)				

The SD candidates are based on reported SD values from clinical trials [21-23](#). For sensitivity analysis a tipping point analysis is planned and based on a penalty for imputed values in the somapacitan arm of 1.8 cm/year this gives a power of 87% (adjusted treatment effect: $0.9*0 - 0.05*1.8 = -0.09$), under the assumption of 5% of subjects not having landmark visit data (corresponding to an analysis that performs an imputation under the non-inferiority null method).²⁴

Primary estimand (EMA)

With the same assumptions as for the other primary estimand presented and Ns from [Table 3](#) above, the different scenarios leads to a conservative power evaluation of 88%-89% for the primary analysis under the hypothetical estimand. For total N=192 the power is calculated to be 88%.

If the per protocol analysis set (PP) is assumed to consist of ~85% of the trial subjects (same proportion across treatment groups), giving 108 subjects in the somapacitan arm and 54 subjects in the Norditropin[®] arm, then repeating the primary analysis based on the primary estimand (hypothetical strategy) on the PP should result in a power of 86% for confirming non-inferiority of somapacitan compared to Norditropin[®], under the assumption of no true treatment difference between the two treatments.

